2.3 Exploratory Objectives

- 2.3.1 To evaluate the acceptability of anal cancer screening among HIV-positive women.
- 2.3.2 To collect data on quality of life and health care costs (including non-direct health care costs and time costs) for an economic evaluation of the cost-effectiveness of anal cancer screening strategies in HIV-positive women.

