38. When you were smoking most heavily, how many cigarettes did you smoke on an average day? (1 pack = 20 cigarettes)

_____ Cigarettes per day

39. For how long did you smoke this heavily? (If time unit is known, indicate the number of years.)

| Code | Years |
|------|---------|
| 98 | Unknown |

COST/TRANSPORTATION QUESTIONS

40. What is the main source of your financial support, including food, rent, and other expenses?
 (Check participant's response. If more than one choice given, PROBE: Is one of these the most important source of your income? If participant answers "No," record all responses given)

| Response | Code |
|-----------------------------------------------------------------|------|
| Own job or salary. | 1 |
| Someone else's job or salary (Specify relationship): _____) | 2 |
| Public assistance, e.g., AFDC, SSI, food stamps | 3 |
| Other (Specify): _____) | 8 |
| Unknown | 98 |

41. Which one best describes your hourly wage or annual income?

| Hourly Wage | Annual Income |
|------------------------|--------------------------|
| \$0.00 - \$4.99 | \$0.00 - \$9,999 |
| \$5.00 - \$7.25 | \$10,000 - \$14,999 |
| \$7.26 - \$9.99 | \$15,000 - \$19,999 |
| \$10.00 - \$14.99 | \$20,000 - \$29,999 |
| \$15.00 - \$19.99 | \$30,000 - \$39,999 |
| \$20.00 - \$24.99 | \$40,000 - \$49,999 |
| \$25.00 - \$29.99 | \$50,000 - \$59,999 |
| \$30.00 - \$34.99 | \$60,000 - \$69,999 |
| \$35.00 - \$39.99 | \$70,000 - \$79,999 |
| \$40.00 - \$49.99 | \$80,000 - \$99,999 |
| More than \$50.00/hour | More than \$100,000/year |

42. Did you miss work today for this visit?

| No | Yes | Not applicable/Don't Work |
|----|-----|---------------------------|
| 0 | 1 | 99 |

43. How did you get to the clinic today?

| Response | Code |
|----------------------------------------------------------------|------|
| Drive yourself | 1 |
| Get a ride from someone else in a personal vehicle | 2 |
| Take public transportation such as the metro bus or metro rail | 3 |
| Take a taxi | 4 |
| Walk or ride bike, or | 5 |
| Get there some other way (SPECIFY) _____ | 6 |
| Decline to answer | 99 |

44. If you took private/public transportation, what was the fare? \$ _____

45. How much time (including travelling time) will you miss from your usual activities because of this appointment?

| Response | Code |
|-------------------------------------------|------|
| Less than 15 minutes | 1 |
| 15 to 30 Minutes | 2 |
| 31 Minutes to 60 Minutes (1 Hour) | 3 |

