| Grade | Code |
|-----------------------------------|------|
| 8 th grade or less | 1 |
| Some high school | 2 |
| High school diploma | 3 |
| Some college or vocational school | 4 |
| Associate degree | 5 |
| College (4 year) degree | 6 |
| Graduate or professional degree | 7 |
| Don't know | 98 |
| Decline to answer | 99 |

**APPENDIX XIV: POST-PROCEDURE TELEPHONE FOLLOW-UP QUESTIONNAIRE
AND SCRIPT**

**Screening HIV-Infected Women for Anal Cancer Precursors
POST PROCEDURE QUESTIONS**

The following questions will be asked **2-5 weeks** after the procedures have been completed via a telephone follow up call, or a visit if preferred by the participant and/or investigator.

Participant ID: 084 - _____ - _____

Date of administration: _____ / _____ / _____

Administered by: _____

Location of administration (e.g. clinic or telephone): _____

Date of last study procedure visit: _____ / _____ / _____

Thank you for agreeing to speak with me today.

I will be asking some personal questions. Most of them are the same or similar to the original questions you answered previously. Again, if you feel uncomfortable answering any question or want to stop at any time, just let me know.

POST PROCEDURE QUESTIONS

1. Did you have bleeding following the last HRA procedure? (If No, skip to question 4.)

| Response | Code |
|----------|------|
| Yes | 1 |
| No | 2 |

2. How many days did you have bleeding? _____ days

3. Did you feel the bleeding was:

| Response | Code |
|----------|------|
| Mild | 1 |
| Moderate | 2 |
| Severe | 3 |

4. Did you have pain following the last HRA procedure? (If No, skip to question 9.)

| Response | Code |
|----------|------|
| Yes | 1 |
| No | 2 |

5. How many days after the HRA procedure did you have pain? _____ days

6. Did you feel the pain was:

| Response | Code |
|----------|------|
| Mild | 1 |
| Moderate | 2 |
| Severe | 3 |

7. Did you take any medication for the pain? (If no, skip to question 9.)

| Response | Code |
|----------|------|
| Yes | 1 |
| No | 2 |

8. And if so, what medication(s)

| Response | Code |
|---------------|------|
| Acetaminophen | 1 |
| NSAIDS | 2 |
| Narcotics | 3 |

9. Did you miss work because of bleeding or pain? (If no, skip to question 12.)

| Response | Code |
|----------|------|
| Yes | 1 |
| No | 2 |

10. If yes, was it because of the:

| Response | Code |
|----------|------|
| Bleeding | 1 |
| Pain | 2 |
| Both | 3 |

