11. How many days did you miss work due to either bleeding or pain? _____ days

12. Did you have any unscheduled visits to any healthcare provider because of bleeding or pain after the HRA?

| Response | Code |
|----------|------|
| Yes | 1 |
| No | 2 |

13. How many times have you had high resolution anoscopy (HRA)? (If only one time, skip to question 15.)

| Response | Code |
|--------------|------|
| 1 time | 1 |
| 2-4 times | 2 |
| 5-10 times | 3 |
| More than 10 | 4 |

14. Comparing your experience with the first (or former) procedure to this most recent procedure, would you say that the most recent procedure was:

| Response | Code |
|--------------|------|
| Better | 1 |
| Same | 2 |
| Worse | 3 |
| I don't know | 98 |

15. Before your recent HRA procedure, how informed were you about the purpose of HRA in screening for anal cancer?

| Response | Code |
|-------------------|------|
| Well informed | 1 |
| Somewhat informed | 2 |
| Poorly informed | 3 |
| I don't know | 98 |

16. Before your recent HRA procedure, how informed were you about any discomfort that you could experience during the procedure?

| Response | Code |
|-------------------|------|
| Well informed | 1 |
| Somewhat informed | 2 |
| Poorly informed | 3 |
| I don't know | 98 |

17. Before your recent HRA procedure, how informed were you about any discomfort/bleeding you might have after the procedure?

| Response | Code |
|-------------------|------|
| Well informed | 1 |
| Somewhat informed | 2 |
| Poorly informed | 3 |
| I don't know | 98 |

18. Before your recent HRA procedure, how informed were you about self-care at home after the procedure?

| Response | Code |
|-------------------|------|
| Well informed | 1 |
| Somewhat informed | 2 |
| Poorly informed | 3 |
| I don't know | 98 |

19. During your recent HRA procedure did you feel supported and well-cared for by the providers who performed the HRA?

| Response | Code |
|--------------|------|
| Yes | 1 |
| No | 2 |
| I don't know | 98 |

20. Some people who have experienced sexual abuse, rape, or other trauma in their lives find the HRA procedure particularly distressing. Have you have had an experience such as these in your lifetime? (IF NO, go to question 22).

| Response | Code |
|--------------|------|
| Yes | 1 |
| No | 2 |
| I don't know | 98 |

21. IF YES, did your most recent HRA procedure cause you to remember the trauma?

| Response | Code |
|----------------|------|
| Yes | 1 |
| No | 2 |
| Not applicable | 97 |

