[from ACTG self report, questions E, H, QL0742(A5257)/ 12-31-08]

27. Are you on HIV medication(s)?

| No (skip to question 29) | Yes | Unsure/ Don't know |
|-----------------------------|-----|-----------------------|
| 0 | 1 | 98 |

28. Rate your **ability** to take all of your HIV medications as specifically prescribed.

| Very poor | Poor | Fair | Good | Very good | Excellent | N/A | Unsure/ Don't know | Decline to answer |
|--------------|------|------|------|--------------|-----------|-----|--------------------------|----------------------|
| 1 | 2 | 3 | 4 | 5 | 6 | 97 | 98 | 99 |

SMOKING QUESTIONS

29. Have you smoked cigarettes in the past 6 months?

| No (skip to question 31) | Yes |
|-----------------------------|-----|
| 0 | 1 |

AMC Smoking

30. On average over the past 6 months, how many cigarettes have you smoked per day? (1 pack equals 20 cigarettes)

_____ (number of cigarettes)

COST/TRANSPORTATION QUESTIONS

31. Which one best describes your hourly wage or annual income?

| Hourly Wage | Annual Income |
|------------------------|--------------------------|
| \$0.00 - \$4.99 | \$0.00 - \$9,999 |
| \$5.00 - \$7.25 | \$10,000 - \$14,999 |
| \$7.26 - \$9.99 | \$15,000 - \$19,999 |
| \$10.00 - \$14.99 | \$20,000 - \$29,999 |
| \$15.00 - \$19.99 | \$30,000 - \$39,999 |
| \$20.00 - \$24.99 | \$40,000 - \$49,999 |
| \$25.00 - \$29.99 | \$50,000 - \$59,999 |
| \$30.00 - \$34.99 | \$60,000 - \$69,999 |
| \$35.00 - \$39.99 | \$70,000 - \$79,999 |
| \$40.00 - \$49.99 | \$80,000 - \$99,999 |
| More than \$50.00/hour | More than \$100,000/year |

32. Did you miss work today for this visit?

| No | Yes |
|----|-----|
| 0 | 1 |

33. How did you get to the clinic today?

| Response | Code |
|----------------------------------------------------------------|------|
| Drive yourself | 1 |
| Get a ride from someone else in a personal vehicle | 2 |
| Take public transportation such as the metro bus or metro rail | 3 |
| Take a taxi | 4 |
| Walk or ride bike, or | 5 |
| Get there some other way (SPECIFY) _____ | 6 |
| Decline to answer | 99 |

34. If you took private/public transportation, what was the fare? \$_____

35. How much time (including travelling time) will you miss from your usual activities because of this appointment?

| Response | Code |
|-------------------------------------------|------|
| Less than 15 minutes | 1 |
| 15 to 30 Minutes | 2 |
| 31 Minutes to 60 Minutes (1 Hour) | 3 |
| 61 Minutes to 90 Minutes | 4 |

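### Time lost after HRA is recorded only as missed work, with no code for women without a job, and the pain-days item can be read in two ways

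*Combined protocol and SAP*

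**What the plan says.** Exploratory objective 2.3.2 is to collect data on quality of life and on "health care costs (including non-direct health care costs and time costs" for an economic evaluation. Section 7.2.2 uses the visit and telephone surveys to describe acceptability, and passes a de-identified dataset that includes costs to an outside group for cost-effectiveness modelling.

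Appendix XIV is administered after each HRA (Visits 1, 3 and 5). Q9 asks "Did you miss work because of bleeding or pain? (If no, skip to question 12". Only a woman who answers Yes reaches Q11: "How many days did you miss work due to either bleeding or pain? _____ days". For symptoms, Q2 asks "How many days did you have bleeding", while the pain counterpart, Q5, asks "How many days after the HRA procedure did you have pain".

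Baseline Q42 (Appendix XIII), on missing work for the visit, has a third response, "Not applicable/Don't Work". The follow-up form repeats the question at Appendix XV Q32, "Did you miss work today for this visit", with No and Yes only. A broader item, baseline Q45, asks "How much time (including travelling time) will you miss from your usual activities because of this appointment", and Appendix XV Q35 repeats it.

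**The concern.** The baseline form recognises that some participants do not work. Q40 also lists someone else's earnings and public assistance as main sources of support. The forms used later drop that distinction just where time lost to the procedure is counted. A No at Q9 can then mean either a worker who lost no time or a woman who had no work to miss. If the second woman could not manage her household or caring tasks for some days after biopsy, no item records it.

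At stake is the time-cost input to the economic evaluation. HRA with at least two biopsies is scheduled up to three times per woman, so recovery time is a plausible part of the burden of screening. The outside group receives de-identified data and cannot return to participants to learn what a No meant.

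Q5 raises a smaller concern. One reading gives the number of days with pain and another gives the day on which pain came. Section 6.3 requires adverse event forms only from Grade 3, so in the supplied forms Q5 is the only structured item on how long milder pain lasted.

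**Working it through.** The plan states no figure to reproduce. The check sets the forms side by side and then shows what the size would depend on.

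**1. Response sets**

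| Item | Subject | Codes | Woman without a job |
|---|---|---|---|
| Appendix XIII Q42 (Visit 1) | Work missed for the visit | 0 No, 1 Yes, 99 not applicable | Has her own code |
| Appendix XV Q32 (Visits 2-5) | Same question | 0 No, 1 Yes | No or blank |
| Appendix XIV Q9 (after each HRA) | Work missed through bleeding or pain | 1 Yes, 2 No; No skips Q10-11 | No or blank |
| Appendix XIII Q45, Appendix XV Q35 | Usual-activity time lost to the appointment | Bands ending at more than 6 hours | Covered, but for the appointment only |

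The usual-activities items are asked at the visit, look ahead and are banded in hours. They do not reach recovery days. Q9-11 are the only items that do, and they are confined to work.

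**2. Can non-workers be identified some other way?**

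- *Call after Visit 1:* yes, largely. Q42 = 99, read with Q40, identifies them a few weeks earlier under the same participant number.
- *Calls after Visits 3 and 5:* not reliably. Q40 is not repeated and Q32 has no such code. Appendix XV Q31 re-asks wage or income but has no option for not working, and annual income need not come from a job. It is a rough proxy.
- *At any call:* knowing that a woman does not work does not recover the days she lost, because they were never asked about.

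**3. What the shortfall depends on**

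Let u be the share of women without a job, D the mean days lost by workers, and r the ratio of non-workers' mean days lost to D. Assume that non-workers are coded No (zero days) and that workers' days are fully captured.

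- Recorded mean over all women: (1 − u) × D
- True mean over all women: (1 − u) × D + u × r × D
- Proportional shortfall: u × r / (1 − u + u × r)

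If r = 1 the shortfall is u. The documents give neither u nor r. With u assumed between 0.20 and 0.60 and r = 1:

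| u | Share of true days recorded | Shortfall |
|---|---|---|
| 0.20 | 80% | 20% |
| 0.40 | 60% | 40% |
| 0.60 | 40% | 60% |

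With r = 0.5 and u = 0.40, the shortfall is 0.20 / 0.80 = 25%. With r = 0 there is none. If non-workers are left blank instead, the mean among those who answered describes workers only, and the blanks cannot be told from ordinary non-response.

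**4. Q5**

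Take a woman with pain on days 1 to 7. Read as duration, the answer is 7. Read as onset, it is 0 or 1. The field keeps only the number, and no interviewer note in the supplied text settles the reading. Section 6.1 allows for pain up to 2 weeks and rarely longer, so the two readings can differ materially.

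**The case against.** The other side has several fair points.

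- *Visit time is already covered for everyone.* This stands. Q45 and Q35 ask all women about usual activities at every visit. The gap is confined to recovery days after HRA.
- *Non-workers can be identified from baseline.* This stands for the Visit 1 HRA. That is the largest round, since every enrolled woman is due one and those with HSIL then leave the study. It weakens for Visits 3 and 5, where work status may have changed, and it does not supply the missing days.
- *Q9-11 may measure missed work correctly among workers, and the documents do not say which kind of time the future model will value.* This also stands. It is a reason to report the two quantities separately, but time that was never collected is not available to value.
- *Q5 sits between a pain yes/no item and a severity item, in parallel with the bleeding block, and a coordinator or nurse can clarify it.* Duration is indeed the likely reading. What remains is a risk of mixed answers.

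A reader might infer that the share missing work would appear to fall from Visit 1 to follow-up because the not-applicable code disappears. The documents do not support that. Suppose half of working women miss work at every visit and 30% to 60% of women work. With all women as the denominator, the share is 0.30 × 50% = 15% to 0.60 × 50% = 30% at every visit. A fall appears only if an analyst removes code 99 from the Visit 1 denominator alone, and section 7.2.2 plans no such comparison.

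**Conclusion.** The point holds as a measurement gap in two exploratory objectives. Recovery time after HRA is collected only as missed work. Women without a job are coded No or left blank, and at Visits 3 and 5 their No cannot be reliably told from that of a worker who lost no time. Time loss across all women is therefore likely understated for objective 2.3.2.

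The size cannot be estimated from the documents. The 20% to 60% range above restates an assumed non-working share, with equal loss in workers and non-workers and a No recorded for every non-worker. It is an illustration of scale, and it would be wrong to cite it as the bias in this study.

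For Q5, a reader might infer that pain duration is mis-measured. The forms show only that the wording permits two readings and that the data could not reveal which was used. Section 7.2.2 names no analysis that sets Q5 against the 2-week statement in section 6.1.

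No primary objective, sample size or power figure is touched. The case for acting is that the correction is nearly free and the missing days cannot be recovered by analysis.

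**What to change.** 1. Appendix XV Q32: restore the not-applicable code as 99, to match baseline Q42.
2. Appendix XIV Q9: add a not-applicable code for women who do not work, as 97, the value that form already uses at Q21.
3. Appendix XIV: add one item, asked of all women, on the number of days they could not do their usual activities because of bleeding or pain.
4. Appendix XIV Q5: use the wording of Q2 with pain in place of bleeding.
5. Reporting: give missed work among working women, and lost usual-activity days among all women.
6. Data already collected: treat Q9 = No in known non-workers as not applicable and not as zero loss, flag the form version, and state the Q5 ambiguity wherever pain days are reported. Carry these notes into the dataset passed to the economic evaluation.

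The cost is a minor revision of two forms and their CRF fields, and slightly longer calls. Answers on the old and new wording should not be pooled without the version flag.

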7.2.2 Exploratory analyses

We will evaluate the acceptability of anal cancer screening based on survey responses regarding participant satisfaction at each study visit ([Appendix XIII](#) and [XV](#)) and phone call surveys ([Appendix XIV](#)) administered after study visits 1, 3,

and 5. Descriptive statistics will be used to characterize participants' acceptability of undergoing anal screening with cytology/HPV and HRA throughout the study to evaluate changes in perceptions. Generalized estimating equations (GEE) will be used to assess acceptability over time adjusting for intrapatient variability. Acceptability will be correlated with clinical and behavioral risk factors, e.g., history of sexual assault, depression, anxiety, medication compliance, sexual behaviors using GEE methods.

A fully de-identified dataset from the study, which will include data obtained on quality of life, anxiety, costs, and procedures, will be made available to [name], MD Anderson, for an economic evaluation of cost effectiveness modeling of anal cancer strategies in HIV-positive women.

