We assure you that your answers will be kept confidential. By providing this information, you will help us a great deal with this study.

Please listen to each question carefully and answer as honestly as possible, even if you only had that type of sexual experience one time. Although some of the behaviors or sexual practices we ask about may be new to you, they are far more common than you may think.

11. Have you ever experienced sexual assault?

| Response | Code |
|-------------------|------|
| Yes | 1 |
| No | 2 |
| I don't know | 98 |
| Decline to answer | 99 |

Sex with Men

The next questions refer only to vaginal sex with men. This is when a man puts his penis, fingers or a sex toy/object in a woman's vagina.

12. Have you ever, any time in your life, had vaginal sex with a man?

| No (skip to question 16) | Yes | Decline to answer (skip to question 16) |
|-----------------------------|-----|--------------------------------------------|
| 0 | 1 | 99 |

13. How many different **men** have you had vaginal sex with **in your entire life**?

| None | 1 | 2-5 | 6-10 | More than 10 | Unsure | Decline to answer |
|------|---|-----|------|--------------|--------|-------------------|
| 0 | 1 | 2 | 3 | 4 | 98 | 99 |

14. How many men have you had vaginal sex with **in the past 6 months**?

| None | 1 | 2-5 | 6-10 | More than 10 | Unsure | Decline to answer |
|------|---|-----|------|--------------|--------|-------------------|
| 0 | 1 | 2 | 3 | 4 | 98 | 99 |

15. How often were condoms used to cover the man's penis, sex toy or object when you had vaginal sex with a man **in the past 6 months**?

| Never | Rarely | Sometimes but less than half | About half the time | More than half the time | Every time | Unsure | Decline to answer |
|-------|--------|------------------------------|---------------------|-------------------------|------------|--------|-------------------|
| 0 | 1 | 2 | 3 | 4 | 5 | 98 | 99 |

Now I am going to ask you questions about anal sex with a man. This is when a man puts his penis, finger, sex toy or object in your anus.

16. Have you **ever**, any time in your life, had anal sex with a man?

| No (skip to question 22) | Yes | Decline to answer (skip to question 22) |
|-----------------------------|-----|--------------------------------------------|
| 0 | 1 | 99 |

17. When was **the last time** a man put his penis in your anus?

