| I don't know | 98 |

22. During your recent HRA procedure did you feel your privacy was respected?

| Response | Code |
|--------------|------|
| Yes | 1 |
| No | 2 |
| I don't know | 98 |

23. How likely would you be to follow recommendations to repeat the HRA procedures?

| Response | Code |
|-------------------|------|
| Very unlikely | 1 |
| Somewhat unlikely | 2 |
| Neutral | 3 |
| Somewhat likely | 4 |
| Very likely | 5 |
| I don't know | 98 |

Please tell me your experience with each of the examinations or procedures. For each of these statements, please tell me whether you **agree** or **disagree**. Then you will be asked if you slightly or strongly agree/disagree with the statement.

24. Anal Pap smear

| Statement | Strongly disagree | Slightly disagree | Neutral | Slightly agree | Strongly agree | Decline to answer |
|-----------------------------------------------------------|-----------------------------|-----------------------------|---------|-------------------|-------------------|----------------------|
| I felt pain during the procedure. | 1 | 2 | 3 | 4 | 5 | 99 |
| I felt uncomfortab le during the exam. | 1 | 2 | 3 | 4 | 5 | 99 |
| I felt at ease. | 1 | 2 | 3 | 4 | 5 | 99 |
| I was prepared to have the procedure. | 1 | 2 | 3 | 4 | 5 | 99 |

25. High resolution anoscopy

| Statement | Strongly disagree | Slightly disagree | Neutral | Slightly agree | Strongly agree | Decline to answer |
|-----------------------------------------------------------|-----------------------------|-----------------------------|---------|-------------------|-------------------|----------------------|
| I felt pain during the procedure. | 1 | 2 | 3 | 4 | 5 | 99 |
| I felt uncomfortab le during the exam. | 1 | 2 | 3 | 4 | 5 | 99 |
| I felt at ease. | 1 | 2 | 3 | 4 | 5 | 99 |
| I was prepared to have the procedure. | 1 | 2 | 3 | 4 | 5 | 99 |

26. Is there anything that will make getting the exam procedures the next time more comfortable for you?

| Response | Code |
|-----------------------------|------|
| Yes | 1 |
| No (Questionnaire complete) | 2 |
| I don't know | 98 |

27. Would any of the following make the next HRA procedure more comfortable for you?

| Response | Yes | No |
|--------------------------------------------------------------------|-----|----|
| More explanation about what to expect from a health care provider. | 1 | 2 |
| Medication to calm my nerves. | 1 | 2 |
| More effective pain medication. | 1 | 2 |

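### In the post-HRA call, trauma questions precede the only post-procedure ratings, so the exploratory association of those ratings with sexual assault is at risk of order bias

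*Combined protocol and SAP*

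**What the plan says.** Appendix XIV is administered after the HRA at Visits 1, 3 and 5. Q1-Q19 cover bleeding, pain, missed work, comparison with an earlier HRA, how well informed the woman was, and support from the providers ("During your recent HRA procedure did you feel supported and well-cared for by the providers who performed the HRA").

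Q20 then opens with a statement, "Some people who have experienced sexual abuse, rape, or other trauma in their lives find the HRA procedure particularly distressing", and asks whether the woman has had such an experience. A No goes to Q22. Q21 reads "IF YES, did your most recent HRA procedure cause you to remember the trauma".

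After that come:
- Q22, "During your recent HRA procedure did you feel your privacy was respected"
- Q23, "How likely would you be to follow recommendations to repeat the HRA procedures"
- the Q24 and Q25 grids on pain, discomfort, ease and preparedness, introduced by "Please tell me your experience with each of the examinations or procedures"
- Q26-Q28 on comfort at the next examination.

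Section 7.2.2 takes acceptability from the visit questionnaires (Appendices XIII and XV) and from these calls. It states: "Acceptability will be correlated with clinical and behavioral risk factors, e.g., history of sexual assault", among other factors, using GEE. Appendix XIII Q11 asks at Visit 1, in neutral words, "Have you ever experienced sexual assault". Appendix XV Q8 asks the same for the past 6 months. Section 2.3.1 lists acceptability as an exploratory objective.

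**The concern.** A question that brings a distressing memory to mind can change the answers that follow it. If every woman received the same prompt, ratings might shift overall but the comparison between groups would be less exposed. Here the recall prompt goes to women who report trauma and is skipped by women who answer No, and trauma history overlaps heavily with the exposure named in 7.2.2. A difference in Q22-Q28 between women with and without a history of sexual assault could then reflect the procedure, the form, or both.

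The order is fixed and no version of the form omits the prompt. A larger sample or a better GEE model therefore cannot separate the two explanations. At stake is how far an exploratory finding about HRA acceptability after sexual assault can be trusted.

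**Working it through.** **1. Order and routing in Appendix XIV**

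| Items | Content | Position |
|---|---|---|
| Q1-Q19 | Side effects, earlier HRA, information, support | Before the prompt |
| Q20 | Statement and trauma question | All women |
| Q21 | Recall of the trauma | Worded for Yes; No skips it |
| Q22 | Privacy | After |
| Q23 | Willingness to repeat HRA | After |
| Q24 | Anal Pap grid | After |
| Q25 | HRA grid | After |
| Q26-Q28 | Comfort next time; No at Q26 ends the form | After |

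Routing for a woman who answers that she does not know at Q20 is unclear: only No carries a skip, yet Q21 is worded for Yes.

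**2. Are there substitutes for Q23-Q25?** The acceptability items in Appendix XIII (Q32-Q34) and Appendix XV (Q24-Q26) stand under a pre-procedure heading and record anticipated concern. Appendix XIV Q1-Q19 do not ask about willingness to repeat HRA and do not contain the rating grids. Q23, Q24 and Q25 have no counterpart elsewhere after the procedure.

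**3. Which data are free of the prompt?** The Visit 1 questionnaire is completed before any call, and Q1-Q19 of the first call precede Q20. At later visits and calls, the statement heard earlier could carry over.

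**4. Exposure item.** Section 7.2.2 names sexual assault but not the source item. Q11 matches that wording and predates every call. Q20 adds other trauma and so is a different variable. Using Q11 does not remove the problem by itself, because a woman positive on Q11 would be expected to answer Yes at Q20 and still receive Q21 before rating.

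**5. Illustration of size.** The documents state no effect size, power or significance level for this analysis, so there is no figure to reproduce. Assumptions: N = 300 completed first calls (the enrolment target), a proportion p = 0.3-0.5 of women exposed, rating SD 1.0-1.3 on a 1-5 scale, no true association, two-sided 0.05.

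SE = SD × √[1/(Np) + 1/(N(1−p))]

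Rejection probability = Φ(δ/SE − 1.96) + Φ(−δ/SE − 1.96), where δ is the shift in points.

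- p = 0.5, SD 1.0: SE = √(1/150 + 1/150) = 0.1155. With δ = 0.2, δ/SE = 1.73 and the probability is 41%.
- p = 0.3, SD 1.3: SE = 1.3 × √(1/90 + 1/210) = 0.1638. With δ = 0.2, δ/SE = 1.22 and the probability is 23%.

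This treats prompted and assault-exposed women as the same group. If the exposure is Q11 and a share q of Q11-negative women also answer Yes at Q20 because of other trauma, the contrast falls to δ(1−q), assuming all Q11-positive women answer Yes:

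- q = 0.3: 0.2 × 0.7 = 0.14 points, giving 14-23%.
- q = 0.5: 0.2 × 0.5 = 0.10 points, giving 9-14%.

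With no shift, the rate is 5%. With 200 calls rather than 300, a shift of 0.2 SD and complete overlap, it is 20.5% at 20% exposed and 29.3% at 50% exposed. Every driver of these figures is assumed.

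**The case against.** Much can be said for the form as it stands. The opening of Q20 may be a considerate lead-in to a sensitive question, and it says only that some people with a trauma history find HRA distressing. A reader might infer that women are told HRA is distressing in general; the text does not say that. A reader might also infer that the prompt comes immediately before the HRA ratings. That fits Q22 and Q23, but Q22-Q24 lie between Q21 and the HRA grid.

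Section 7.2.2 names no principal acceptability item and draws on several questionnaires, so the prompt does not reach all of the acceptability data. Nothing says that Q20 will be the exposure, and Q11 and Appendix XV Q8 already ask about sexual assault neutrally. The objective is exploratory, assault is one of several example correlates, and no significance level is set.

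All of this stands, and it limits the reach and severity of the point. It does not answer the core of it. The items that follow the prompt are the only ones of their kind, no text addresses order effects, and the prompt still depends on something close to the exposure.

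**Conclusion.** The point holds as a risk, not as a demonstrated bias. For Q22-Q28, an association with sexual assault could be partly produced by question order, and the data as collected could not show otherwise. The documents support neither a size nor a direction: an order effect could create an association, or hide or exaggerate a real one.

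A reader might go further and conclude that the whole planned association is biased, or that the percentages above are its false-positive rate. Neither follows. Q1-Q19 of the first call and the Visit 1 items precede the prompt. The percentages depend on an assumed shift, exposure proportion, SD, overlap between prompted and exposed women, and number of completed calls.

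Severity is low: the objective is exploratory and no primary estimate is affected. The change is still worth making because it is cheap and analysis cannot repair the problem afterwards.

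**What to change.** - **Form.** Move Q20-Q21 to directly after Q25 and before Q26. Change the Q20 skip so that No leads to Q26, and state the routing for women who do not know. Do not place them after Q28: No at Q26 ends the questionnaire, so those women would never be asked, and missing trauma data would depend on acceptability.
- **Section 7.2.2.** Name Appendix XIII Q11 as the sexual-assault exposure, with Appendix XV Q8 for new events.
- **If calls have already been made.** Record the form version for each call, and add a sensitivity analysis limited to first-call items asked before Q20. It can support the result for those items but cannot replace Q23-Q25.

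The cost is a form revision, a short addition to 7.2.2 and a version flag, with no new items or participants. Two limits remain: Q26-Q28 would still follow the prompt, and the statement heard at one call could carry over to later visits and calls.
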